8.2. Exclusion Criteria

Individuals meeting any of the following criteria at Screening or Baseline are ineligible to participate in the study:

1) Subjects with any unstable primary mood disorder (DSM-5 criteria) at Screening.

- 2) Subjects who have unstable medical illness or clinically significant abnormalities on laboratory tests, or ECG at Screening as determined by the Principal Investigator.
- 3) Subjects with a significant risk of committing suicide based on history, routine psychiatric status examination, investigator's judgment, or who had an answer of "yes" on any question other than 1–3 (currently or within the past 30 days) on the baseline/screening version of the C-SSRS.
- 4) Subjects with a clinical presentation at Screening and/or history consistent with another neurologic condition that may have had accompanying abnormal movements (e.g., Huntington's disease, Parkinson's disease, Wilson's disease, stroke, Restless Legs Syndrome).
- 5) Female subjects who are currently pregnant or lactating or planning to become pregnant during the course of the study.
- 6) Subjects who have moderate to severe renal insufficiency at Screening.
- 7) Subjects who have hepatic impairment at Screening.
- 8) Subjects with current or recent (past 3 months) history of DSM-5 substance use disorder (with the exception of nicotine).
- 9) Subjects with positive urine drug screen for cocaine, amphetamine, methamphetamine, benzodiazepines, barbiturates, phencyclidine (PCP) or opiates at Screening except those receiving stable, prescribed treatment for ADHD.
- 10) Subjects with \geq 25% absolute change in YGTSS-TTS score between the Screening Visit and Baseline visit assessments.
- 11) Subjects with a lifetime history of bipolar disorder type I or II, dementia, schizophrenia, or any other psychotic disorder.
- 12) Subjects with a major depressive episode in the past 2 years.
- 13) Subjects with a history of attempted suicide.
- 14) Subjects with a history of seizures (excluding febrile seizures that occurred <2 years prior to Screening).
- 15) Subjects with history of neuroleptic malignant syndrome.
- 16) Subjects with a myocardial infarction within 6 months.
- 17) Subjects who have had previous treatment with ecopipam.
- 18) Subjects who have had previous treatment with:
 - a. investigational medication within 1 month prior to Screening
 - b. depot neuroleptics within 3 months prior to Screening
 - c. oral neuroleptics within 4 weeks prior to Screening

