- 19) Subjects receiving anti-depressant, anti-anxiety or anti-ADHD medications unless the dosage has been stable for a minimum of 4 weeks prior to Screening and not prescribed to relieve the neurological symptoms related to TS.
- 20) Subjects who have a need for medications which would have unfavorable interactions with ecopipam, e.g., dopamine antagonists or agonists [including bupropion], tetrabenazine, monoamine oxidase inhibitors, or St. John's Wort.
- 21) Initiation or changes in behavioral therapies for TS during the course of the study (i.e., Habit Reversal Training or Comprehensive Behavioral Intervention for Tics) as well as deep brain stimulation.
- 22) Subjects who have initiated new behavior therapies fewer than 10 weeks prior to Baseline visit.

- 23) Subjects unable to swallow tablets.
- 24) Subjects with a known hypersensitivity to ecopipam or any of its excipients.
- 25) Any subject who in the opinion of the investigator is not a suitable candidate for the study.

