9.3. Prohibited Therapies

Since ecopipam and its metabolite (SCH40853) may inhibit CYP2D6, OATP1B1, PGP and UGT1A9, for any drug that is a substrate of these enzymes, the label for the drug should be consulted to decide if a dose adjustment is needed. Drugs that are strong inducers of these enzymes are prohibited. An illustrative list of such drugs is provided in the Prohibited Medications List in the Appendices.

Prohibited therapies per the exclusion criteria (Section 8.2) include:

- Previous treatment with ecopipam
- Any investigational medication within 1 month prior to Screening
- Depot neuroleptics within 3 months prior to Screening
- Oral neuroleptics within 4 weeks prior to Screening

- Current use of anti-depressant, anti-anxiety or anti-ADHD medications unless the dosage has been stable for a minimum of 4 weeks prior to Screening and are not prescribed to relieve the neurological symptoms related to TS
- Medications which would have unfavorable interactions with ecopipam, e.g., dopamine antagonists or agonists (including bupropion), tetrabenazine, monoamine oxidase inhibitors, or St. John's Wort
- Initiation or changes in behavioral therapies for TS during the course of the study (i.e., Habit Reversal Training or Comprehensive Behavioral Intervention for Tics) as well as deep brain stimulation
- New behavior therapies to treat TS that were initiated fewer than 10 weeks prior to the Baseline visit

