- Intrauterine hormone-releasing system (IUS)
- Bilateral tubal occlusion
- Vasectomized male partner
 - Vasectomised partner is a highly effective birth control method provided that partner is the sole sexual partner of the woman of childbearing potential study participant and that the vasectomised partner has received medical assessment of the surgical success.
- Sexual abstinence (defined as refraining from heterosexual intercourse during the entire period of exposure associated with the study treatment).
 - In the context of this guidance, sexual abstinence is considered a highly effective method only if defined as refraining from heterosexual intercourse during the entire period of risk associated with the study treatments. The reliability of sexual abstinence needs to be evaluated in relation to the duration of the clinical study and the preferred and usual lifestyle of the subject.

Adapted from: Clinical Trials Facilitation Group (CTFG). Recommendations Related to Contraception and Pregnancy Testing in Clinical Trials. September 15, 2014.

Available at: https://www.hma.eu/fileadmin/dateien/Human_Medicines/01- About_HMA/Working_Groups/CTFG/2014_09_HMA_CTFG_Contraception.pdf

PROHIBITED MEDICATIONS LIST

Examples below are not exclusive.

- Any new stimulant for the treatment of ADHD that the subject was not taking at randomization is also prohibited.
- Other medications used to treat TS are prohibited.
- Dopamine depleting medications are prohibited.
- D2 receptor antagonists prohibited.

Prohibited Antipsychotic Medications	
Aripiprazole	Loxapine
Cisapride	Methylphenidate
Clonidine	Paliperidone
Dextroamphetamine	Pimozide
Dronedarone	Risperidone
Droperidol	Thioridazine
Fluoxetine	Topiramate
Guanfacine	Ziprasidone
Haloperidol	

Other Prohibited Medications for the Treatment of Tics	Mechanism
Any dopamine agonist (e.g., ropinirole, pramipexole)	
Baclofen	GABA-B receptor agonist
Clonazepam	GABA-A receptor positive allosteric modulation
Duetetrabenazine	VMAT2 inhibitor / monoamine depleter
Guanfacine	Alpha-2A adrenergic receptor agonist
Reserpine	VMAT1/2 inhibitor / inhibits uptake of dopamine
Tetrabenazine	VMAT2 inhibitor / monoamine depleter
Valbenazine	VMAT2 inhibitor / monoamine depleter

Other Prohibited Medications	Mechanism
Chloroethylnorapomorphine	D2 receptor antagonist
Chlorpromazine	D2 receptor antagonist/ antipsychotic
Cinnarizine	Antihistamine/ calcium channel blocker/ Interaction with D2 receptors

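### The appendix bans methylphenidate and dextroamphetamine outright, although exclusion 19 admits children on stable ADHD medication

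*Protocol*

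**What the plan says.** Eligibility is set in Protocol Section 8.2. Exclusion 19 bars "Subjects receiving anti-depressant, anti-anxiety or anti-ADHD medications unless the dosage has been stable for a minimum of 4 weeks prior to Screening"; a second condition is that the drug is not given for the neurological symptoms of TS. The Synopsis carries the same criterion. Section 9.3, which lists the therapies prohibited under the exclusion criteria, repeats it: "Current use of anti-depressant, anti-anxiety or anti-ADHD medications unless the dosage has been stable for a minimum of 4 weeks prior to Screening". Exclusion 9 bars a positive urine drug screen "except those receiving stable, prescribed treatment for ADHD".

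The Prohibited Medications List in the appendices opens with "Examples below are not exclusive" and a set of bullets, one of which reads "Any new stimulant for the treatment of ADHD that the subject was not taking at randomization is also prohibited". The table "Prohibited Antipsychotic Medications" follows. Methylphenidate, dextroamphetamine and fluoxetine are among its entries, and none carries a footnote, dose or duration condition.

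Section 9.3 refers to the appendix once: "An illustrative list of such drugs is provided in the Prohibited Medications List in the Appendices". That sentence comes directly after the prohibition of strong enzyme inducers.

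**The concern.** A site cannot follow both the table and exclusion 19 for a child who takes a stable stimulant for ADHD. Under exclusion 19 the child may enter and stay on treatment. Under the table the child is on a prohibited drug.

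Section 5.1 names ADHD first among the common co-morbid conditions, and the Synopsis plans about 60 sites, so the question can arise at many of them. One site might enrol the child, a second might turn the child away, and a third might stop a treatment that the eligibility criteria allow to continue. At stake are who gets in, and whether children's existing treatment is disturbed without need. The efficacy test is not at stake.

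**Working it through.** No power, alpha or event figure is involved, so the check sets the texts side by side. One assumption comes from general knowledge, because the documents do not state drug classes: methylphenidate and dextroamphetamine are ADHD stimulants, and fluoxetine is an antidepressant.

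**Size of the conflict in the table.** The table has 9 entries in the left column and 8 in the right: 9 + 8 = 17. The two stimulants make 2 of 17. Fluoxetine is 1 of 17 and is treated separately. None of the three is among the 12 entries of the strong-inducer table or the 8 entries of the tic-treatment table, so neither list explains why they are banned.

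**Three rules for one stimulant.**

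| Child | Exclusion 19 and Section 9.3 | Appendix bullet | Appendix table |
|---|---|---|---|
| A. Stable dose for at least 4 weeks before Screening, for ADHD | allowed | not caught | prohibited |
| B. Started 1 week before Screening, still taken at randomization | not allowed | not caught | prohibited |
| C. Started after randomization | not allowed | prohibited | prohibited |

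Child A shows the direct contradiction: the table alone says no. Child B shows a second mismatch: the bullet's cut-off is randomization, while exclusion 19's is 4 weeks before Screening. Correcting the table alone would leave two stimulant rules in force.

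**How strongly each text contradicts the table.**
- Exclusion 19: directly, for both stimulants. Section 9.3 restates it and is not a second rule.
- Appendix bullet: by implication. A ban on new stimulants suggests that existing ones may continue, but the word 'also' can be read as adding to the table.
- Exclusion 9: by implication, and for dextroamphetamine only. The screen names amphetamine and methamphetamine but not methylphenidate, and the clause waives a positive test rather than permitting a drug.

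**Washout rules.** Footnote a of Table 2 places screening procedures after washout of applicable medications without naming them. Other criteria do. Inclusion 8 covers drugs for motor or vocal tics (14 days before Baseline). Exclusion 18 covers oral neuroleptics (4 weeks), depot neuroleptics (3 months) and investigational drugs (1 month), each before Screening. Neither reaches a stable stimulant given for ADHD, so the table is the outlier.

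**Analysis.** SAP Section 4.1.1 puts both use of prohibited medication and dose change of allowed medication under treatment policy, with observed Week 12 data. Labelling a child's stimulant as one or the other leaves the primary estimate unchanged.

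**The case against.** The strongest reply is that no careful site would be misled. Eligibility is decided in Sections 8.1 and 8.2, and 8.2 does not refer to the appendix. Section 9.3 calls the appendix illustrative. The bullet on new stimulants stands above the table, and the table's heading names a drug class to which stimulants do not belong. To turn away child A, a site would have to set an explicit criterion aside in favour of a list under the wrong heading. This stands as a reason to keep the point small. It does not remove the contradiction: the illustrative wording is attached to strong inducers, the table's heading says prohibited, and nothing ranks the two texts.

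It could also be argued that exclusion 20 already covers stimulants, since it bars "medications which would have unfavorable interactions with ecopipam, e.g., dopamine antagonists or agonists [including bupropion], tetrabenazine, monoamine oxidase inhibitors" and its list is open-ended. But it names no stimulant, and that reading would leave the ADHD exception in exclusion 9 with little purpose.

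A reader might infer three stronger points that the documents do not support:
- That four independent texts contradict the table. Only exclusion 19 does so directly; Section 9.3 repeats it, and the other two do so by implication.
- That fluoxetine is a third error. Its listing is at odds with exclusion 19's allowance for stable antidepressants, but exclusion 20 leaves room for a drug-specific bar. The appendix also treats such drugs one by one: paroxetine, venlafaxine and atomoxetine appear as dose-adjustment items. The entry may be intended.
- That sites have no guidance on what to wash out. Inclusion 8 and exclusion 18 give it.

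**Conclusion.** The two stimulant entries are wrong as written. They directly contradict one eligibility rule, exclusion 19, and no order of precedence resolves the conflict. The size is 2 of 17 table entries; the number of children affected is unknown and may be small. Fluoxetine is an open question for the sponsor.

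The primary mITT estimate, alpha and the planned 150 subjects are unaffected. A reader might infer that per-protocol membership would differ from site to site. The documents do not support that: SAP Section 5.4 settles exclusions in one blinded review by the sponsor's clinical team before unblinding, and SAP Section 5.6 leaves the categories to a deviation plan that is not among the documents. Any per-protocol effect is therefore unknown.

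The conclusion rests on the stated drug classes and on Section 8.2 expressing the intended rule. The washout criteria and the appendix's own bullet both point that way.

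**What to change.** 1. Remove methylphenidate and dextroamphetamine from the table, or add to each: unless at a stable dose for at least 4 weeks before Screening and not prescribed for TS symptoms.
2. Reword the stimulant bullet to the same cut-off, so that randomization no longer serves as a separate one.
3. Add one sentence stating that Section 8.2 prevails over the appendix for medications at entry.
4. Ask the sponsor about fluoxetine: either qualify it in the same way, or state that a drug-specific ban is intended.
5. Use the corrected list when deviations are classified at the blinded review.

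The cost is a minor protocol correction and a memo to sites, with IRB or IEC handling where local rules require it (Protocol Section 16.1). Sample size, visits and the analysis model do not change.

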PP	Per-Protocol
SAE	serious adverse event
SAP	Statistical Analysis Plan
SD	standard deviation
SNAP-IV	Swanson, Nolan, and Pelham questionnaire
SS	Safety Set
TEAE	Treatment emergent adverse event
TS	Tourette's Syndrome
TTS	Total Tic Score
YGTSS-TTS	Yale Global Tic Severity Scale-Total Tic Score

2. Purpose

The purpose of this statistical analysis plan (SAP) is to ensure that the data listings, summary tables, and figures which will be produced, and the statistical methodologies that will be used, are complete and appropriate to allow valid conclusions regarding the study objectives.

2.1. Responsibilities

Syneos Health will perform the statistical analyses and are responsible for the production and quality control of all tables, figures, and listings.

2.2. Timings of Analyses

The primary analysis of safety and efficacy and/or pharmacokinetics is planned after all subjects complete the final study visit or terminate early from the study.

Interim analyses will be completed in coordination with the Data Safety Monitoring Board (DSMB) meetings to primarily assess safety and preliminary efficacy. An interim analysis will be conducted after approximately 50% of subjects have enrolled and completed treatment or early termination procedures are completed. See Section 11 for complete details.

3. Study Objectives

3.1. Primary Objective

The primary objective of this study is to evaluate the efficacy of ecopipam tablets in pediatric subjects (aged \geq 6 to <18 years) with Tourette's Syndrome (TS).

3.2. Secondary Objective(s)

The secondary objectives of this study are to evaluate the safety of ecopipam tablets in pediatric subjects (aged ≥ 6 to <18 years) with TS and characterize the pharmacokinetics (PK) of ecopipam.

3.3. Brief Description

This is a multicenter, placebo-controlled, double-blind, randomized, parallel-group, Phase 2b study in pediatric subjects (aged \geq 6 to <18 years) with TS. Following a Screening period up to 28 days and Baseline visit, eligible subjects will be randomized 1:1 to receive either a target steady-state dose of 2 mg/kg/day ecopipam HCl or matching placebo for a 4-week Titration period followed by an 8-week Treatment period. Following titration, subjects who weigh \geq 18 kg to \leq 23 kg will receive a 37.5-mg active dose (or placebo), subjects who weigh >23 kg to \leq 34 kg will receive a 50-mg active dose (or placebo), subjects who weigh >34 kg to \leq 44 kg will receive a 75-mg active dose (or placebo), subjects who weigh >44 kg to \leq 68 kg will receive a 100-mg active dose (or placebo), subjects who weigh >68 kg to \leq 83 kg will receive a 150-mg active dose (or placebo), and subjects who weigh >83 kg will receive a 200-mg active dose (or placebo).

After the Screening period, subjects will return to the clinic at Baseline and at 4, 6, 8, and 12 weeks after Randomization. Subjects will have telephone visits on Weeks 2 and 10 to assess adverse events and other safety parameters. Efficacy assessments will be conducted at Weeks 4, 6, 8, and 12 and safety assessments will be conducted at all visits as well. A Follow Up visit will be conducted in the clinic 7 and 14 days after the last dose of study medication. Subjects will also be contacted 30 days after the last dose of study medication to determine any adverse events. At study completion or early termination, subjects will be tapered off study drug as outlined in the protocol.

3.4. Subject Selection

3.4.1. Inclusion Criteria

Subjects eligible for inclusion in this study must fulfill all of the criteria listed in section 8.1 of the protocol.

3.4.2. Exclusion Criteria

Subjects will not be eligible if they meet any of the criteria listed in section 8.2 of the protocol.

3.5. Determination of Sample Size

A sample size of 75 subjects per group will provide >80% power to detect difference between groups of 3 points on change from baseline the Yale Global Tic Severity Scale-Total Tic Score (YGTSS-TTS), with standard deviation = 6.1 and alpha = 0.05, assuming 10% drop out.

3.6. Treatment Assignment & Blinding

Subjects will be randomized 1:1 to either ecopipam or matching placebo. Randomization will be stratified by weight band (\geq 18 to \leq 23 kg, >23 to \leq 34 kg, >34 to \leq 44 kg, >44 to \leq 68 kg, >68 to \leq 83 kg, >83 kg).

Throughout the study, subjects and all personnel involved with the conduct and interpretation of the study, including the subject, parents/guardians, investigators, site personnel, and sponsor staff will be blinded to the treatment codes. Randomization data will be kept strictly confidential, filed securely by an appropriate group with the Sponsor or Syneos and accessible only to authorized persons (e.g., Safety) until the time of unblinding.

A master list of all treatments and the subject numbers associated with them will be maintained electronically by the unblinded clinical supply vendor and the unblinded personnel at Syneos. The process to request unblinding and the randomization code will be outlined in a separate document. The site will be trained in this process and it should be used only in an emergency. These codes should only be broken if knowledge of the subject's randomization code will affect his/her medical treatment. If possible, before breaking the blind, the Investigator should consult with the Sponsor to ascertain the necessity of breaking the code. The Investigator is to record the date and time of requesting the code and the reason for breaking the code.

3.7. Administration of Study Medication

During the 4-week titration period, the following ecopipam HCI doses or matching placebo will be administered oral (per os) (PO) for each of the weight bands:

- Those who weigh ≥18-≤23 kg will titrate from 12.5 mg daily to 37.5 mg daily: 12.5 mg during Week 1, 25 mg during Week 2, and 37.5 mg during Weeks 3 and 4.
- Those who weigh >23-<34 kg will titrate from 12.5 mg daily to 50 mg daily: 12.5 mg during Week 1, 25 mg during Week 2, 37.5 mg during Week 3 and 50 mg during Week 4.
- Those who weigh >34-<44 kg will titrate from 12.5 mg daily to 75 mg daily: 12.5 mg during week 1, 25 mg during week 2, 50 mg during Week 3 and 75 mg during Week 4.
- Those who weigh >44-<68 kg will titrate from 25 mg daily to 100 mg daily: 25 mg during Week 1, 50 mg during Week 2, 75 mg during Week 3 and 100 mg during Week 4.
- Those who weigh >68-<83 kg will titrate from 25 mg daily to 150 mg daily: 25 mg during Week 1, 50 mg during Week 2, 100 mg during Week 3 and 150 mg during Week 4.
- Those who weigh >83 kg will titrate from 25 mg daily to 200 mg daily: 25 mg during Week 1, 50 mg during Week 2, 100 mg during Week 3, and 200 mg during Week 4.

Subjects who do not tolerate the dose titration up to the full designated dose for their weight stratum will be discontinued from the study. These subjects will also be tapered off their current dose of study drug according to their weight stratum.

During the 8-week treatment phase, the following ecopipam HCI doses or matching placebo will be administered for each of the weight bands:

- Those who weigh ≥18-≤23 kg will receive 37.5 mg daily.
- Those who weigh >23-≤34 kg will receive 50 mg daily.
- Those who weigh >34-≤44 kg will receive 75 mg daily.
- Those who weigh >44-≤68 kg will receive 100 mg daily.
- Those who weigh >68-≤83 kg will receive 150 mg daily.

Those who weigh >83 kg will receive 200 mg daily.

All doses will be administered PO once daily in the evening. Subjects who have changes in weight during the study will not have their doses adjusted for the duration of the study.

At the end of the 8-week treatment phase, subjects will titrate off therapy and receive ecopipam HCI doses or matching placebo that will be reduced by 25 mg/day until off of study drug. Signs of symptoms of withdrawal will be monitored.

3.8. Study Procedures and Flowchart

After the screening period, subjects will return to the clinic at Baseline and 4, 6, 8 and 12 weeks after Randomization. Subjects will have telephone visits on Weeks 2 and 10 to assess adverse events and other safety parameters. Efficacy assessments will be conducted at weeks 4, 6, 8 and 12. Safety assessments will be conducted at these visits as well. A Follow Up visit will be conducted in the clinic 7 and 14 days after the last dose of study medication. Subjects will also be contacted 30 days after the last dose of study medication to determine any adverse events. At study completion or early termination, subjects will be tapered off study drug as outlined in the protocol. See Appendix section 14.1 for the Study of Assessments Flowchart.

4. Endpoints

